**3. Subject Information**

Subject ID # \_\_\_\_\_ Subject Gender:  Female  Male Subject DOB: mm \_\_\_\_ / dd \_\_\_\_ / yyyy \_\_\_\_

**4. Amgen Product Exposure**

Amgen Product	Dose at time of conception	Frequency	Route	Start Date
				mm / dd / yyyy

Was the Amgen product (or study drug) discontinued?  Yes  No  
If yes, provide product (or study drug) stop date: mm \_\_\_\_ / dd \_\_\_\_ / yyyy \_\_\_\_  
Did the subject withdraw from the study?  Yes  No

**5. Pregnancy Information**

Pregnant female's LMP mm \_\_\_\_ / dd \_\_\_\_ / yyyy \_\_\_\_  Unknown  
Estimated date of delivery mm \_\_\_\_ / dd \_\_\_\_ / yyyy \_\_\_\_  Unknown  N/A  
If N/A, date of termination (actual or planned) mm \_\_\_\_ / dd \_\_\_\_ / yyyy \_\_\_\_  
Has the pregnant female already delivered?  Yes  No  Unknown  N/A  
If yes, provide date of delivery: mm \_\_\_\_ / dd \_\_\_\_ / yyyy \_\_\_\_  
Was the infant healthy?  Yes  No  Unknown  N/A  
If any Adverse Event was experienced by the infant, provide brief details:  
\_\_\_\_\_  
\_\_\_\_\_

**Form Completed by:**

Print Name: \_\_\_\_\_ Title: \_\_\_\_\_  
Signature: \_\_\_\_\_ Date: \_\_\_\_\_

[Print Form](#)

**AMGEN® Lactation Notification Worksheet**

Fax Completed Form to the Country-respective Safety Fax Line  
SELECT OR TYPE IN A FAX#

**1. Case Administrative Information**

Protocol/Study Number: \_\_\_\_\_

Study Design:  Interventional  Observational (If Observational:  Prospective  Retrospective)

**2. Contact Information**

Investigator Name \_\_\_\_\_ Site # \_\_\_\_\_

Phone (\_\_\_\_) \_\_\_\_\_ Fax (\_\_\_\_) \_\_\_\_\_ Email \_\_\_\_\_

Institution \_\_\_\_\_

Address \_\_\_\_\_

**3. Subject Information**

Subject ID # \_\_\_\_\_ Subject Date of Birth: mm \_\_\_\_ / dd \_\_\_\_ / yyyy \_\_\_\_

**4. Amgen Product Exposure**

Amgen Product	Dose at time of breast feeding	Frequency	Route	Start Date
				mm ____ / dd ____ / yyyy ____

Was the Amgen product (or study drug) discontinued?  Yes  No

If yes, provide product (or study drug) stop date: mm \_\_\_\_ / dd \_\_\_\_ / yyyy \_\_\_\_

Did the subject withdraw from the study?  Yes  No

**5. Breast Feeding Information**

Did the mother breastfeed or provide the infant with pumped breast milk while actively taking an Amgen product?  Yes  No

If No, provide stop date: mm \_\_\_\_ / dd \_\_\_\_ / yyyy \_\_\_\_

Infant date of birth: mm \_\_\_\_ / dd \_\_\_\_ / yyyy \_\_\_\_

Infant gender:  Female  Male

Is the infant healthy?  Yes  No  Unknown  N/A

If any Adverse Event was experienced by the mother or the infant, provide brief details: \_\_\_\_\_

**Form Completed by:**

Print Name: \_\_\_\_\_ Title: \_\_\_\_\_

Signature: \_\_\_\_\_ Date: \_\_\_\_\_

[figure not shown]
#### Appendix 6. Sample Storage and Destruction

Any blood (eg, biomarker, PK) sample collected according to the Schedule of Activities ([Table 2-1](#)) can be analyzed for any of the tests outlined in the protocol and for any tests necessary to minimize risks to study subjects. This includes testing to ensure analytical methods produce reliable and valid data throughout the course of the study. This can also include, but is not limited to, investigation of unexpected results, incurred sample reanalysis, and analyses for method transfer and comparability.

All samples and associated results will be coded prior to being shipped from the site for analysis or storage. Samples will be tracked using a unique identifier that is assigned to the samples for the study. Results are stored in a secure database to ensure confidentiality.

If informed consent is provided by the subject, Amgen can do additional testing on remaining samples (ie, residual and back-up) to investigate and better understand the study indications (eg, migraine), neurological diseases, and/or AMG 301 immunogenicity, and/or in the identification of subjects who may have positive or negative responses to AMG 301, and characterize aspects of the molecule (eg, mechanism of action/target, metabolites). Results from this analysis are to be documented and maintained, but are not necessarily reported as part of this study. Samples can be retained for up to 20 years.

CCI

The subject retains the right to request that the sample material be destroyed by contacting the investigator. Following the request from the subject, the investigator is to provide the sponsor with the required study and subject number so that any remaining [sample types (eg, blood, tumor)] samples and any other components from the cells can be located and destroyed. Samples will be destroyed once all protocol-defined procedures are completed. However, information collected from samples prior to the request for destruction, will be retained by Amgen.

The sponsor is the exclusive owner of any data, discoveries, or derivative materials from the sample materials and is responsible for the destruction of the sample(s) at the

request of the subject through the investigator, at the end of the storage period, or as appropriate (eg, the scientific rationale for experimentation with a certain sample type no longer justifies keeping the sample). If a commercial product is developed from this research project, the sponsor owns the commercial product. The subject has no commercial rights to such product and has no commercial rights to the data, information, discoveries, or derivative materials gained or produced from the sample. See [Appendix 3](#) for subject confidentiality.

## **Appendix 7. Hepatotoxicity Stopping Rules: Suggested Actions and Follow-up Assessments and Study Treatment Rechallenge Guidelines**

Subjects with abnormal hepatic laboratory values (ie, alkaline phosphatase [ALP], aspartate aminotransferase [AST], alanine aminotransferase [ALT], total bilirubin [TBL]) and/or international normalized ratio (INR) and/or signs/symptoms of hepatitis (as described below) may meet the criteria for withholding or permanent discontinuation of Amgen investigational product or other protocol-required therapies, as specified in the [Guidance for Industry Drug-Induced Liver Injury: Premarketing Clinical Evaluation, July 2009](#).

### **Criteria for Withholding and/or Permanent Discontinuation of Amgen Investigational Product and Other Protocol-required Therapies Due to Potential Hepatotoxicity**

The following stopping and/or withholding rules apply to subjects for whom another cause of their changes in liver biomarkers (TBL, INR, and transaminases) has not been identified.

Important alternative causes for elevated AST/ALT and/or TBL values include, but are not limited to:

- Hepatobiliary tract disease
- Viral hepatitis (eg, hepatitis A/B/C/D/E, Epstein-Barr Virus, cytomegalovirus, herpes simplex virus, varicella, toxoplasmosis, and parvovirus)
- Right sided heart failure, hypotension or any cause of hypoxia to the liver causing ischemia
- Exposure to hepatotoxic agents/drugs or hepatotoxins, including herbal and dietary supplements, plants and mushrooms
- Heritable disorders causing impaired glucuronidation (eg, Gilbert's syndrome, Crigler-Najjar syndrome) and drugs that inhibit bilirubin glucuronidation (eg, indinavir, atazanavir)
- Alpha-one antitrypsin deficiency
- Alcoholic hepatitis
- Autoimmune hepatitis
- Wilson's disease and hemochromatosis
- Nonalcoholic fatty liver disease including steatohepatitis (NASH)
- Non-hepatic causes (eg, rhabdomylosis, hemolysis)

If investigational product(s) is/are withheld, the subject is to be followed for possible DILI according to recommendations in the last section of this appendix.

Rechallenge may be considered if an alternative cause for impaired liver tests (ALT, AST, ALP) and/or elevated TBL, is discovered and the laboratory abnormalities resolve to normal or baseline (see next section in this appendix).

**Table 12-2. Conditions for Withholding and/or Permanent Discontinuation of Amgen Investigational Product and Other Protocol-required Therapies Due to Potential Hepatotoxicity**

Analyte	Temporary Withholding	Permanent Discontinuation
TBL	> 3x ULN at any time	> 2x ULN OR
INR	--	> 1.5x ULN (for subjects not on anticoagulation therapy) AND
AST/ALT	> 8x ULN at any time > 5x ULN but < 8x ULN for $\geq$ 2 weeks > 5x ULN but < 8x ULN and unable to adhere to enhanced monitoring schedule > 3x ULN with clinical signs or symptoms that are consistent with hepatitis (such as right upper quadrant pain/tenderness, fever, nausea, vomiting, and jaundice)	In the presence of no important alternative causes for elevated AST/ALT and/or TBL values > 3x ULN (when baseline was < ULN)
ALP	OR > 8x ULN at any time	--

ALP = alkaline phosphatase; ALT = alanine aminotransferase; AST = aspartate aminotransferase;  
INR = international normalized ratio; TBL = total bilirubin; ULN = upper limit of normal

**Criteria for Rechallenge of Amgen Investigational Product and Other Protocol-required Therapies After Potential Hepatotoxicity**

The decision to rechallenge the subject is to be discussed and agreed upon unanimously by the subject, investigator, and Amgen.

If signs or symptoms recur with rechallenge, then Amgen investigational product and other protocol-required therapies, as appropriate is to be permanently discontinued. Subjects who clearly meet the criteria for permanent discontinuation (as described in [Table 12-2](#)) are never to be rechallenged.

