## 2.2 Schedule of Activities

**Table 2-1. Schedule of Activities**

Procedure	Screening Period (Up to 7 weeks)			Double-Blind Treatment Period a (12 weeks) (± 2 days)									Safety Follow-up Period (16 weeks) (± 5 days)			
	Screening up to 3 weeks	Baseline Period b		Day 1 (Post- rand) c	Wk 1	Wk 2	Wk 4	Wk 6	Wk 8	Wk 9	Wk 10	Wk 12/ET d	Wk 16	Wk 20	Wk 24	Wk 28/ET/ EOS d
		-4 Weeks	Pre- rand (Day 1)													
GENERAL AND SAFETY ASSESSMENTS																
Informed consent	X															
Physical examination	X												X			X
Height and Weight e	X		X										X			X
Demographics f	X															
Vital signs g	X	X	X h	X i		X	X	X	X		X	X	X	X	X	X
Medical and Medication history j	X		X													
12-lead ECG	X			X						X			X		X	X
Adverse events k	X	X	X	X	X	X	X	X	X	X	X	X	X	X	X	X
Concomitant medications	X			X	X	X	X	X	X	X	X	X	X	X	X	X
Product Complaints Recording				X		X	X	X	X		X					
LABORATORY ASSESSMENTS																
Serum pregnancy test l	X															
Urine Pregnancy test l			X					X		X			X			X

Page 1 of 3

Footnotes defined on last page of table

Table 2-1. Schedule of Activities

Procedure	Screening Period (Up to 7 weeks)			Double-Blind Treatment Period a (12 weeks) (± 2 days)									Safety Follow-up Period (16 weeks) (± 5 days)			
	Screening up to 3 weeks	Baseline Period b		Day 1 (Post- rand) c	Wk 1	Wk 2	Wk 4	Wk 6	Wk 8	Wk 9	Wk 10	Wk 12/ET d	Wk 16	Wk 20	Wk 24	Wk 28/ET/ EOS d
		-4 Weeks	Pre- rand (Day 1)													
Hepatitis B and Hepatitis C storage sample				X m												
Serum plasma glucose n	X															
HbA1c	X								X o				X o		X o	X o
Hematology, chemistry	X			X			X	X o				X o		X		X
Urinalysis	X											X				
Urine drug screen p	X															
RANDOMIZATION/INVESTIGATIONAL PRODUCT DOSING																
Call to IVR/IWR system q	X			X			X	X	X	X		X				X
Entry into the Baseline period		X														
Randomization			X													
Investigational Product				X r		X	X	X	X		X					
PK ASSESSMENTS																
PK Sampling (serum) s				X	X		X		X	X	X	X	X	X	X	X
BIOMARKER ASSESSMENTS																

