### Other Medical Conditions

205 Currently diagnosed with chronic pain syndromes (eg, fibromyalgia, chronic back pain, chronic pelvic pain)

206 History of major psychiatric disorder, (such as schizophrenia and bipolar disorder), or current evidence of depression based on a Beck Depression Inventory II (BDI-II) total score > 19 at screening. Subjects with anxiety disorder and/or major depressive disorder are permitted in the study if the investigator considers the subject to be stable (with BDI-II  $\leq$  19) and are taking no more than 1 medication for each disorder. Subjects must have been on a stable dose within the 2 months before the start of the baseline period.

207 History of seizure disorder or other significant neurological conditions other than migraine. Note: A single childhood febrile seizure is not exclusionary.

208 Malignancy within the 5 years before screening, except non-melanoma skin cancers, cervical or breast ductal carcinoma in situ.

209 Known human immunodeficiency virus infection by history

210 Hepatic disease by history or total bilirubin  $\geq$  1.5 x upper limit of normal (ULN) or alanine aminotransferase (ALT) or aspartate aminotransferase (AST)  $\geq$  2.0 x ULN, as assessed by the central laboratory at screening.

211 Glycosylated hemoglobin (HbA1c)  $\geq$  6.0% at screening

212 **Serum plasma glucose level  $\geq$  100 mg/dL at screening; ideally performed while fasting**

213 History of diabetes mellitus or history of impaired fasting glucose

- 214 Body mass index (BMI) ≤ 18.0 or ≥ 40 at screening
- 215 Poorly controlled hypertension (systolic blood pressure 150 mmHg and/or diastolic blood pressure 90 mmHg or greater)
- 216 Myocardial infarction, stroke, transient ischemic attack, unstable angina, or coronary artery bypass surgery or other revascularization procedure within 12 months before screening
- 217 History or evidence of any other unstable or clinically significant medical condition that, in the opinion of the investigator, would pose a risk to subject safety or interfere with the study evaluation, procedures, or completion
- 218 Subject has any clinically significant vital sign, laboratory, or electrocardiogram (ECG) abnormality during screening that, in the opinion of the investigator, could pose a risk to subject safety or interfere with the study evaluation

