## Drug-induced Liver Injury Reporting and Additional Assessments

### Reporting

To facilitate appropriate monitoring for signals of DILI, cases of concurrent AST or ALT and TBL and/or INR elevation, according to the criteria specified in the above, require the following:

- The event is to be reported to Amgen as a serious adverse event within 24 hours of discovery or notification of the event (ie, before additional etiologic investigations have been concluded)
- The appropriate CRF (eg, Event CRF) that captures information necessary to facilitate the evaluation of treatment-emergent liver abnormalities is to be completed and sent to Amgen

Other events of hepatotoxicity and potential DILI are to be reported as serious adverse events if they meet the criteria for a serious adverse event defined in [Appendix 4](#).

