5.3 Study Points of Reference

Baseline Period

The 4-week baseline period starts when the subject has met all Part 1 eligibility criteria (refer to Section 6.1 of the protocol) and is entered in the baseline period (refer to Section 6.6 of the protocol) and ends when the subject is considered a screen failure (discontinuation before randomization and/or subject does not meet all baseline eligibility criteria, refer to [Section 6.3](#)) or randomized.

The first day of the baseline period is the day that the subject records the first assessment in the eDiary and the last day of this period is the date the subject records the last assessment prior to the first dose of IP on Study Day 1.

The baseline assessment is defined as the last non-missing measurement for the endpoint of interest taken before the first dose of IP. In cases where baseline measurements are taken on the same day as the first dose of IP, it will be assumed that these measurements are taken prior to IP being administered. For subjects who are randomized but not dosed after the randomization, the baseline of the study is defined as the last non-missing measurement prior to or on the date of randomization. Above definition applies to safety measurements and PROs collected at office **visits** (HIT-6, CAPS and MMIDAS).

For measurements with multiple individual items such as C-SSRS and ECG, all individual items from the same set of measurement will be used for analysis. If some items from the same set are missing, then the latest complete set of measurement prior to the first dose of IP will be used as baseline. A similar rule holds for post-baseline measurements.

Baseline assessment of data collected from eDiary will be summarized as monthly measurements using data collected during baseline period.

Study Day 1

Study Day 1 is defined as the first IP dose date. For subjects who are randomized but not dosed after randomization, the Study Day 1 is defined as the date of randomization.

Study Day

Study Day is defined as the number of days from Study Day 1.

Before Study Day 1:

Study Day = (date of interest – date of Study Day 1)

On or after Study Day 1:

Study Day = (date of interest – date of Study Day 1) + 1

Therefore the day prior to Study Day 1 is -1.

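### Table 12-2's only permanent-stop rule cannot fire when baseline AST and ALT are both at or above ULN, and in a defined range no hold applies either

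*Protocol*

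**What the plan says.** **Permanent discontinuation (Protocol, Appendix 7, Table 12-2).** The TBL row requires more than 2x ULN and ends in OR. The INR row reads "> 1.5x ULN (for subjects not on anticoagulation therapy) AND". The AST/ALT row reads "> 3x ULN (when baseline was < ULN" and adds that no other important cause is present. No other permanent-discontinuation condition appears.

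**Temporary withholding (same table).** Any one of these suffices:
- TBL above 3x ULN
- AST/ALT above 8x ULN
- AST/ALT between 5x and 8x ULN for at least 2 weeks, or with enhanced monitoring not followed
- AST/ALT above 3x ULN with signs or symptoms of hepatitis
- ALP above 8x ULN

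INR has no withholding criterion.

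**What hangs on the table.** Subjects who clearly meet its permanent criteria "are never to be rechallenged". Concurrent elevations, "according to the criteria specified in the above, require the following", must be reported as a serious adverse event within 24 hours. A general route remains: "Other events of hepatotoxicity and potential DILI are to be reported as serious adverse events if they meet the criteria".

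**Close observation (Appendix 7).** AST or ALT above 3x ULN, or a doubling from a raised pre-drug value, triggers repeat tests within 24 hours. Retesting is then every 24 hours while TBL exceeds 2x ULN or INR exceeds 1.5, until values improve, with a search for other causes.

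**Who can have a raised baseline.** Criterion 210 (Protocol 6.2) excludes AST or ALT only from "2.0 x ULN, as assessed by the central laboratory at screening". The "Hematology, chemistry" row of Table 2-1 is marked at screening, Day 1 and weeks 4, 6, 12, 20 and 28. For values taken on the day of first dose, SAP 5.3 states that "it will be assumed that these measurements are taken prior to IP being administered". A Day 1 result can therefore be the baseline, and criterion 210 does not limit it.

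**The concern.** The qualifier removes one group of eligible subjects from the only required stop, and nothing replaces it. Appendix 7 does recognise raised pre-drug values, but only as a reason for close observation. Two subjects with identical on-treatment results are then handled differently on baseline alone.

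For the subject left out, three things are lost: the required stop, the rechallenge bar tied to Table 12-2 and, on a literal reading of the reporting paragraph, the automatic 24-hour report. Close observation does not replace the stop, because testing may become less frequent once values stabilise even if product has not been discontinued.

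The SAP takes a different approach. Its liver table in 9.6.3 counts AST or ALT above 3x ULN with TBL at or above 2x ULN and ALP below 2x ULN, whatever the baseline. It can count a subject whom the stopping rule passes over. The data are kept; the required action is not.

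**Working it through.** No plan figure exists to reproduce. The check applies the printed rules to defined laboratory states.

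**Step 1. Two readings of the permanent rule** (b = baseline AST/ALT as a multiple of ULN).
- Reading A: (TBL > 2 or INR > 1.5) and (AST/ALT > 3 with b < 1).
- Reading B, strict precedence: TBL > 2, or (INR > 1.5 and AST/ALT > 3 with b < 1).

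Reading A is more natural for two reasons. The Appendix 7 reporting text speaks of concurrent elevations of transaminases and TBL and/or INR. Reading B would also make the separate TBL > 3x hold redundant, since product would already have stopped at 2x.

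**Step 2. The uncovered range under reading A, with b at or above 1 for both enzymes.** All of these hold:
- TBL > 2x or INR > 1.5x ULN (not on anticoagulation)
- TBL at or below 3x and ALP at or below 8x ULN
- no signs or symptoms of hepatitis
- AST/ALT above 3x up to 5x ULN, or above 5x and below 8x for under 2 weeks with monitoring followed

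**Step 3. Worked case:** ALT 4.5x, TBL 2.5x ULN, symptom-free, ALP normal.

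| Baseline AST and ALT | Permanent stop (A) | Hold | Close observation |
|---|---|---|---|
| 0.99x ULN | yes | no | yes |
| 1.0x ULN | no | no | yes |

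**Step 4. Grid inside that range.** AST/ALT takes 7 levels (3.1, 3.5, 4, 4.5, 5, 6, 7x), TBL 6 (1, 1.5, 2, 2.1, 2.5, 3x) and INR 4 (1, 1.5, 1.6, 2.5x). ALP is 1x.
- TBL/INR pairs with TBL > 2 or INR > 1.5: 24 − (3 × 2) = 18. States per baseline: 18 × 7 = 126.
- Seven baselines from 1.0x to 1.99x: 126 × 7 = 882 states. Under reading A, 882 have neither stop nor hold.
- Two baselines below ULN (0.5x, 0.99x): 126 × 2 = 252 states, none uncovered.
- Under reading B, the uncovered states are those with TBL at or below 2x and INR > 1.5x: 3 × 2 pairs × 7 × 7 = 294 of 882.

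A wider grid of 280 cells (AST/ALT 2.5x to 12x, TBL 1x to 4x, INR 1 to 3) agrees. Under reading A the permanent rule fires in 192 cells at baseline 0.9x ULN and in 0 at 1.0x, 1.2x or 1.9x. Every uncovered cell meets the close-observation trigger.

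**Step 5. Doses still scheduled** (Protocol 7.1.1: Day 1 and weeks 2, 4, 6, 8, 10).
- Week 4 result: 3 of 6 visits remain. In the 420 mg Q2W arm, 3 × 420 = 1,260 of 6 × 420 = 2,520 mg. In the 210 mg Q4W arm, only week 8 is active: 210 of 3 × 210 = 630 mg.
- Week 6 result: 2 visits remain, 2 × 420 = 840 mg or 210 mg.

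These are upper bounds. They assume the state persists without symptoms and nobody stops product by judgement.

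**The case against.** Several points on the other side stand and narrow the claim.

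- **Precedence.** Read strictly, TBL above 2x ULN alone stops product at any baseline, and the worked case is then covered. Only the INR limb stays open. INR is not a scheduled analyte in Table 12-1, so an INR value obtained under the protocol would normally come from a subject already under close observation.
- **AST and ALT separately.** A subject with one enzyme below ULN at baseline can still qualify through that enzyme. The gap is complete only when both are raised.
- **The grid is definitional.** It was restricted to states that escape every hold, so 882 of 882 restates the gap and gives no frequency.
- **Persistence.** The 6x and 7x levels (2/7 of 882 = 252 states) meet the 2-week hold if they last, roughly at the next dosing visit.
- **Symptoms.** AST/ALT above 3x ULN with nausea or vomiting triggers a hold at any baseline, and both are also migraine symptoms.
- **Other protection.** The investigator may stop product for severe related events (7.4.3.1), 8.1 allows removal for adverse events, and the Data Review Team watches safety (10.4.2). Other medically important events are serious and reportable within 24 hours, so little reporting may be lost in practice. Criteria 210, 217, 218 and 233 also screen out known liver disease and abnormalities judged clinically significant.
- **Status of the appendix.** Its title calls the actions suggested, although its text sets out stopping and withholding rules. The table also shows extraction damage around the AST/ALT and ALP rows.
- **Threshold choice.** Some would prefer a threshold relative to baseline. A rise from 1.99x to 3.1x ULN is only about 1.6-fold (3.1 / 1.99).

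None of this supplies a required stop or hold for the worked case under reading A. The qualifier is explicit text and does not depend on cell layout. Nor is it needed to protect subjects whose abnormality has another explanation, because the rules already exclude identified alternative causes.

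**Conclusion.** The gap is real and should be fixed. It rests on reading A, on AST and ALT both being at or above ULN at baseline, and on the symptom-free range in step 2 of the working. Under strict precedence it shrinks to INR above 1.5x ULN with TBL at or below 2x ULN.

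A reader might infer more than the documents support:
- *That these subjects go unmonitored.* They do not; daily retesting and cause work-up apply.
- *That they would keep receiving product.* The plan does not require a stop or hold, but it permits stopping throughout.
- *That the grid or dose figures measure how often this happens.* The documents give no count of subjects with raised baselines. The number is likely small.
- *That liver signals would be lost from the report.* The SAP liver table keeps them.

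The effect is confined to safety action in rare cases and does not touch the efficacy conclusions. The case for change is that the potential consequence is serious and the correction is cheap.

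**What to change.** Check the layout of Table 12-2 in the source PDF first. Then delete the baseline qualifier, so that AST/ALT above 3x ULN with TBL above 2x ULN or INR above 1.5x ULN, unexplained, requires permanent discontinuation at any baseline. State the AND/OR grouping explicitly. On the grid this leaves 0 of 882 states uncovered.

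If the sponsor prefers a baseline-relative threshold for the permanent stop, add at minimum a mandatory temporary hold for these concurrent elevations at any baseline. Without the hold, a rule of above 3x ULN and at least 2x baseline still leaves 108 of 882 states open: 6 baseline-by-AST/ALT combinations × 18 TBL/INR pairs. These occur where twice a baseline of 1.6x to 1.99x ULN (3.2x to 3.98x) exceeds the observed value.

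In either case, point the rechallenge bar and the 24-hour reporting paragraph in Appendix 7 to the completed rule.

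The cost is one phrase, or one added hold, and two cross-references, with no new tests. The downside is that a few raised-baseline subjects may stop or pause product who would otherwise continue, including one whose Day 1 AST/ALT was already above 3x ULN if TBL or INR then rises.
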